**Exclusion Criteria** The following will exclude patients from study participation Myocardial infarction within 6 months of registration Brain metastases unless documented to be controlled post completion of local therapy (surgery and/or radiation therapy) for at least four weeks prior to registration Pregnant or breast feeding women. Women with child bearing potential must use effective measures to prevent pregnancy while receiving pegylated liposomal doxorubicin Have a concurrent active non-breast malignancy except for non-melanoma skin cancer Have a concurrent active non-breast malignancy except for non-melanoma skin cancer Her2 positive tumors as defined by FDA guidelines (3+ immunohistochemical staining, defined as uniform, intense membrane staining of more than 10% of invasive tumor cells, and for cases with 2+ staining showing gene amplification by FISH, expressed as a ratio of more than 2 when comparing HER-2 gene and chromosome 17 fluorescent signals)

**Intervention:** Patients with metastatic breast cancer treated at the University of Arizona Cancer Center and University of New Mexico Cancer center will be enrolled in this trial. Patients whose treatment for their tumor includes liposomal doxorubicin are eligible to take part in this study. Their primary tumors will be obtained for evaluation of BRCA1 protein expression. When primary tumor is not available, paraffin embedded metastatic tumor will be tested for BRCA1 protein expression. Patients will receive pegylated liposomal doxorubicin intravenously at  $30\text{mg}/\text{m}^2$  every 21 days.

**Duration of Intervention:** Patients will get a baseline PET/CT or CT chest/abdomen/pelvis scan prior to receiving pegylated liposomal doxorubicin. We will repeat the same imaging scan at 9-12 weeks to evaluate response by RECIST 1.1. Pegylated liposomal doxorubicin will be stopped if there is evidence of disease progression. Also, it will be discontinued if there is development of persistent  $\geq$  grade 3 fatigue or non-reversible  $\geq$  grade 4 hematological or renal or liver abnormalities or if the patient chooses.

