#### **Analytic plan for secondary objective:**

The progression free survival in patients with low BRCA1 protein expression and intact BRCA1 protein expression will be analyzed by Kaplan-Meier methodology. The results will be summarized by 25th, 50th (median), and 75th percentiles with associated 2-sided 95% confidence intervals,

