### 3.3. **Study Duration and Follow up**

All patients will be treated with pegylated liposomal doxorubicin until evidence of tumor progression. Patients will get a baseline CT or PET/CT scan prior to receiving pegylated liposomal doxorubicin. Repeat imaging at week 9 -12 ( $\pm$  7 days) will be performed to evaluate response. Subsequent imaging schedule will be left to the treating physician's discretion. All patients will be treated until documented disease progression, intolerable toxicity or withdrawal of consent.

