## 4. **Selection and Withdrawal of Patients**

### 4.1. **Inclusion Criteria:**

To be eligible for inclusion, each patient must have:

- 4.1.1 Metastatic breast cancer and have formalin-fixed, paraffin-embedded tumor available for testing BRCA1 protein expression
- 4.1.2 Adults over 18 years of age
- 4.1.3 Have resolution of all acute toxic effects of any prior chemotherapy or radiotherapy to NCI CTC grade  $\leq$  1 prior to study registration.
- 4.1.4 Be informed of the investigational nature of this study and provide written informed consent in accordance with institutional and federal guidelines prior to study specific screening procedures
- 4.1.5 Be willing and able to comply with the treatment plan, scheduled clinic visits, laboratory and oncological tests and other study procedures
- 4.1.6 Have a ECOG performance status of 0 – 2
- 4.1.7 Measurable disease by CT by RECIST 1.1 to evaluate response. Patients with bone only lesions are also eligible to enroll. Criteria to monitor for response will be based on non-target lesions per RECIST criteria
- 4.1.8 Adequate bone marrow function defined as platelets  $\geq$   $100 \times 10^9$  cells/L, neutrophils  $\geq$   $1.5 \times 10^9$  cells/L, white blood cells (WBC)  $\geq$   $3.0 \times 10^9$  cells/L and a hemoglobin  $\geq$  90 gm/L
- 4.1.9 Liver function tests (AST and/ or ALT) should be  $\leq$  2 x upper limit of normal (ULN, defined as per laboratory where blood testing is done), total bilirubin  $\leq$  1.5 x ULN (except for patients with liver metastases, ALT and/or ALT  $\leq$  5 times the upper limit of normal is accepted)
- 4.1.10 Patients who are already on pegylated liposomal doxorubicin will be eligible to participate in this study as long as they meet the other inclusion/exclusion criteria and can sign informed consent

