#### 4.4. **Patient Registration**

Data for patients enrolled on interventional trials must be entered per current practices into the Oncore electronic clinical trials management system.

University of Arizona Cancer Center

Patients must be registered prior to initiation of treatment. Patients will be registered through a Breast Team Clinical Research Coordinator (CRC) from 8:00 a.m. to 5:00 p.m., Mountain Standard Time, Monday through Friday, (excluding holidays)

University of New Mexico Cancer Center

Patients must be registered prior to initiation of treatment. Prior to registration, eligibility criteria must be confirmed with the UNM CC Clinical Research Office. If the patient meets the eligibility criteria he/she will be assigned a **unique patient study number** by the Clinical Research Office as further detailed below.

The patient will be registered in the Oncore System using the study number.

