#### **Registration Guidelines**

Before a subject participates in the trial, the investigator or delegate is responsible for obtaining written informed consent after adequate explanation of the aims, methods, anticipated benefits, subject responsibilities and potential hazards of the study and before any protocol-specific screening procedures or any study required medications are administered. All patients must be registered before the start of treatment.

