**Evaluation overall**  
The best response is from the start treatment and imaging done weeks (± 7

6.2.5 **Response rate:** The clinical response rate is the percentage of evaluable patients who achieve complete response (CR) or partial response (PR) as the best overall response.

6.2.6 **Progression-free survival:** will be measured as the time from the start of pegylated liposomal doxorubicin to the time the patient is first recorded as having disease progression or dies. If a patient does not progress or die while being followed via tumor assessment, progression-free survival will be censored at the time of last disease assessment.

7. **Study Drug Information**

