### 8.3. **Analytic plan for secondary objective:**

**Definition of secondary endpoints:** Progression free survival will be measured as the times from the start of pegylated liposomal doxorubicin to the time the patient is first recorded as having disease progression or dies. If a patient does not progress or die while being followed via tumor assessment, progression-free survival will be censored at the time of last disease assessment.

We will calculate the median progression free survival in patients with low BRCA1 and normal BRCA1 protein expression. Median progression free survival will be estimated by Kaplan-Meier methodology.

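### Section 4.1.10 admits patients already on the drug although registration must precede treatment; if they enrol, median PFS counted from drug start is biased upward

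*Combined protocol and SAP*

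**What the plan says.** - **Eligibility.** Section 4.1.10, repeated in the synopsis: "Patients who are already on pegylated liposomal doxorubicin will be eligible to participate in this study", provided the other criteria are met and consent can be given. No limit on cycles or time on drug is stated. The interim-analysis text in section 8.2 adds that, if the normal-BRCA1 cohort closes, patients under treatment with the drug will continue to be consented.
- **Registration.** Section 4.4, for each site: "Patients must be registered prior to initiation of treatment". Registration Guidelines in section 5.2: "All patients must be registered before the start of treatment". Neither gives an exception.
- **PFS.** Section 6.2.6 counts "time from the start of pegylated liposomal doxorubicin to the time the patient is first recorded as having disease progression" or death. Section 8.3: "Median progression free survival will be estimated by Kaplan-Meier methodology". The synopsis likewise says PFS "will be analyzed by Kaplan-Meier methodology". No delayed entry or landmark is mentioned.
- **Baseline scan.** Section 3.3: "Patients will get a baseline CT or PET/CT scan prior to receiving pegylated liposomal doxorubicin". The synopsis (Duration of Intervention) and section 6.2.1 agree that baseline precedes the drug. Section 5.1 places staging within 28 days of registration. Appendix 2 allows baseline evaluations at most 4 weeks before treatment.
- **Response.** The response rate (sections 3.1, 6.2.5 and 8.2) and the Simon counts of 12 and 35 (section 8.2) refer to evaluable patients.

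**The concern.** Taken literally, the registration rule leaves 4.1.10 admitting nobody; taken the other way, every patient admitted under 4.1.10 breaches the registration rule.

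The statistical consequence follows if such patients do enrol. The synopsis says the drug is stopped at progression, so a patient who progressed or died before registration can no longer enter as someone already on it. Those who do enter bring a stretch of follow-up in which an event was impossible. Ordinary Kaplan-Meier from drug start places them in the risk set from time zero, so the curve is too high and the median too long. The same selection can raise the response rate, which feeds the Simon decision in the normal-BRCA1 cohort.

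**Working it through.** **1. The plan's own design figure.** Simon design: 12 patients, continue if at least 2 respond, 35 in total, positive if at least 6 respond. With X1 ~ Bin(12, p) and X2 ~ Bin(23, p), P(positive) = sum over x from 2 to 12 of P(X1 = x) × P(X2 ≥ 6 − x). This gives 0.098 at p = 0.10 and 0.901 at p = 0.30. The stated 0.10/0.10 design reproduces and is not in dispute.

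**2. How late can entry be?** If one scan must both precede the drug (3.3, 6.2.1) and fall within 28 days of registration (5.1), the drug cannot have started more than about 4 weeks before registration. Appendix 2 also ties that scan to drug start. So the scan rules imply a cap of about 4 weeks, which 4.1.10 does not state.

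**3. PFS.** Inputs: true median m = 2.5 months (the reference figure in the synopsis background), which is 10.87 weeks, and an exponential shape (assumption). A share f enters at week w, and R is the fraction not yet excluded at w. For times after w the naive curve is S(t) × k, with k = (1 − f) + f/R. Setting it to 0.5 gives naive median = m × (1 + log2 k).

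At w = 4 the exponential model gives R = 2^(−4/10.87) = 0.775, so 22.5% are excluded. That is probably too many. Progression counts when first recorded, and the first planned scan is nominally at week 9 (6.2.2) or weeks 9-12 (3.3), each ± 7 days. Before week 4 only death, clinical progression or an unscheduled scan can exclude a patient. I therefore also take R = 0.90 and 0.95 (assumptions).

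| Excluded by week 4 | f = 20% | f = 30% | f = 50% |
|---|---|---|---|
| 22.5% | 2.70 | 2.80 | 2.99 |
| 10% | 2.58 | 2.62 | 2.70 |
| 5% | 2.54 | 2.56 | 2.59 |

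Example: f = 0.30, R = 0.775 gives k = 0.70 + 0.30/0.775 = 1.087 and 2.5 × (1 + 0.1205) = 2.80 months. With entry spread evenly over weeks 0-4 under the exponential model, the medians are 2.60, 2.65 and 2.74. Entry at week 9 would give 3.02-3.68, but only if the scan rules were breached.

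**4. Response, pre-drug baseline.** If every excluded patient would have been a non-responder, the apparent rate is p × k. At true p = 0.10 and f = 0.30:

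| Excluded by week 4 | Apparent rate | Type I error |
|---|---|---|
| none | 0.100 | 0.098 |
| 5% | 0.102 | 0.103 |
| 10% | 0.103 | 0.110 |
| 22.5% | 0.109 | 0.131 |

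**5. Response, on-drug baseline (a breach of 3.3 and 6.2.1).** If 30% of entrants' responses were missed because shrinkage preceded the baseline, with f = 0.30 and no selection, the rate at true 0.10 is 0.7 × 0.10 + 0.3 × 0.10 × 0.7 = 0.091. Type I error is then 0.069 and power 0.853. With full selection they are 0.088 and 0.888.

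**6. Difference between cohorts.** With true medians of 2.5 and 5.0 months (illustrative), f = 0.30 in both and the exponential model at week 4, the naive medians are 2.80 and 5.29. The difference is 2.49 instead of 2.50; the ratio falls from 2.00 to 1.89.

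**7. Does delayed entry work?** Simulated with f = 0.30, entry at week 4, exponential, no censoring. At n = 15 the typical median is 2.5 months (5th-95th percentile 1.1-4.4) against 2.8 (1.6-4.6) for the naive estimate, with RMSE 1.02 against 1.03. At n = 35, RMSE is 0.63 against 0.70.

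**The case against.** The strongest reply is that 4.1.10 is an explicit eligibility criterion, while sections 4.4 and 5.2 are procedure and can be read as referring to treatment on study. That softens the wording conflict but does not touch the PFS bias, because the clock still starts at the first dose.

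The second reply concerns size, and it stands. The exponential figures assume far more loss by week 4 than a schedule with its first scan at about week 9 would detect; with 5-10% lost, the excess is at most 0.2 months. PFS is also secondary, descriptive and untested.

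A reader might infer more than the documents support in four ways:

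- **That the response rate could move either way under the plan.** It cannot if the pre-drug baseline rule is followed. The downward shift in step 5 needs an on-drug scan as baseline.
- **That 0.131 is a ceiling on type I error at a 30% share.** It is a model value. It pairs a true 10% response rate with a 2.5-month median that was reported alongside 25%. A 2.0-month median in the same formula gives 0.141.
- **That the BRCA1 contrast is undermined.** With entrants spread evenly, the difference in medians hardly changes. Tumours are batch-tested after enrolment, so there is no evident reason for uneven shares unless the normal cohort closes early.
- **That the Appendix 2 reporting text makes all eligible patients the main response analysis.** The endpoint and Simon counts are defined in evaluable patients; the appendix is general RECIST wording.

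**Conclusion.** The point holds as a contradiction to reconcile and as a PFS bias of known direction but uncertain, probably modest, size. If patients already on the drug enrol, the planned median is too long: about 0.2-0.5 months under the exponential model at week 4, and up to about 0.2 months if early exclusions are 5-10%. These ranges rest on assumed shares of 20-50%, a true median of 2.5 months and entry at the implied 4-week cap; if nobody enters late, there is no bias. Simon type I error would be about 0.10-0.13 at a 30% share, against 0.098 as designed. Confidence is high in the conflict and the direction of the PFS bias, and low in any single magnitude. It should be fixed because the remedy is cheap.

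**What to change.** Choose one option and make every passage agree with it.

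**Option A: registration before treatment is kept.** Delete 4.1.10 and its synopsis copy, and reword the section 8.2 sentence on consenting patients under treatment, which would otherwise leave the conflict in place. The Simon characteristics of 0.098 and 0.901 then need no qualification on this account.

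**Option B: such patients stay eligible, or some are already enrolled.**
- Amend section 4.4 and the Registration Guidelines to say so, and state in 4.1.10 the exposure limit that the scan rules already imply.
- Record both the drug-start date and the registration date.
- State that only the pre-drug scan may serve as RECIST baseline for these patients.
- Estimate PFS by Kaplan-Meier from drug start with delayed entry at registration (left truncation).
- Keep the primary response analysis and the Simon counts in evaluable patients, and add a sensitivity result, by BRCA1 cohort, in those registered before first dose. Do not move the Simon decision to that subset without replacing patients: with 12 then about 25 in total (35 × 0.7 = 24.5) and unchanged cut-offs, power falls from 0.90 to 0.78.

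**Cost.** Option A may slow accrual slightly. Option B needs a short amendment, one extra date field and a sentence in the analysis plan, and gives slightly less precision early on the curve. In the cohort of about 15, delayed entry at week 4 removes the bias without reducing RMSE; the gain there is a correctly centred median.

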### 4.2. **Exclusion Criteria**

The following will exclude patients from study participation:

- 4.2.1. Myocardial infarction within 6 months of registration
- 4.2.2. Brain metastases unless documented to be controlled post completion of local therapy (surgery and/or radiation therapy) for at least four weeks prior to registration
- 4.2.3. Pregnant or breast feeding women. Women with child bearing potential must use effective measures to prevent pregnancy while receiving pegylated liposomal doxorubicin
- 4.2.4. Have a concurrent active non-breast malignancy except for non-melanoma skin cancer

- 4.2.5. Her2 positive tumors as defined by FDA guidelines(3+ immunohistochemical staining, defined as uniform, intense membrane staining of more than 10% of invasive tumor cells, and for cases with 2+ staining showing gene amplification by FISH, expressed as a ratio of more than 2 when comparing HER-2 gene and chromosome 17 fluorescent signals)

#### 4.3. **Study Exit**

Patients will continue with study visits until study exit. Patients will exit the study at tumor progression or withdrawal. Each patient has the right to withdraw from the study at any time without prejudice. Should a patient withdraw from the study prior to disease progression, the reason(s) must be stated on the case report form. All procedures (vital signs, laboratory evaluations, physical examination, tumor response, adverse events and concomitant medications) should be performed at the study exit visit. All enrolled patients will be followed for 30 days after week 9 visit.

Patients may be withdrawn from the study early due to:

- a. Development of toxicity which in the Investigator's judgment precludes further study participation
- b. Significant protocol violations or noncompliance on the part of the patient or Investigator
- c. Discontinuation, in the judgment of the Investigator, is in the patient's best interest
- d. The patient is beginning another treatment
- e. Refusal of the patient to continue treatment or follow-up
- f. Loss to follow-up
- g. Pregnancy

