### 5.3. **Treatment Phase**

The following tests and observations will be performed during the treatment phase of

the study.

Test	Interval
Physical exam	No less than every 8 weeks
Complete blood counts and ANC and platelet count	No less than every 4 weeks
Liver function panel to include total bilirubin	No less than every 4 weeks
Serum creatinine	No less than every 4 weeks
Repeat disease assessment with physical exam and repeat imaging test that showed measured pretreatment	No less than every 9 weeks

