#### 5.4. **Follow Up**

Patients will be followed according to the institutional standard guidelines. We will only follow patients who have experienced grade 3 or 4 adverse event or serious adverse event that are possible/probably or definitely related to the study required medication for 30 days after the week 9 visit.

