### Evaluation of best overall response

- The best overall response is the best response recorded from the start of the treatment until disease progression/recurrence (taking as reference for PD the smallest measurements recorded since the treatment started). In general, the patient's best response assignment will depend on the achievement of both measurement and confirmation criteria.

Target lesions	Non-Target lesions	New Lesions	Overall response
CR	CR	No	CR
CR	Non-CR/non-PD	No	PR
CR	Not evaluated	No	PR

PR	Non-PD or not all evaluated	No	PR
SD	Non-PD or not all evaluated	No	SD
PD	Any	Yes or No	PD
Any	PD	Yes or No	PD
Any	Any	Yes	PD

- Patients with a global deterioration of health status requiring discontinuation of treatment without objective evidence of disease progression at that time should be classified as having “symptomatic deterioration”. Every effort should be made to document the objective progression even after discontinuation of treatment.
- In some circumstances it may be difficult to distinguish residual disease from normal tissue. When the evaluation of complete response depends on this determination, it is recommended that the residual lesion be investigated (fine needle aspirate/biopsy) to confirm the complete response status.

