### **Reporting of results**

- All patients included in the study must be assessed for response to treatment, even if there are major protocol treatment deviations or if they are ineligible. Each patient will be assigned one of the following categories: 1) complete response, 2) partial response, 3) stable disease, 4) progressive disease, 5) early death from malignant disease, 6) early death from toxicity, 7) early death because of other cause, or 9) unknown (not assessable, insufficient data).
- All of the patients who met the eligibility criteria should be included in the main analysis of the response rate. Patients in response categories 4-9 should be considered as failing to respond to treatment (disease progression). Thus, an incorrect treatment schedule or drug administration does not result in exclusion from the analysis of the response rate. Precise definitions for categories 4-9 will be protocol specific.
- All conclusions should be based on all eligible patients.

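### Section 4.3 turns several reasons for stopping treatment into study exit with no defined efficacy follow-up, so PFS may be censored informatively

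*Combined protocol and SAP*

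**What the plan says.** **Exit.** Section 4.3: "Patients will exit the study at tumor progression or withdrawal". Its list of reasons for early withdrawal from the study includes toxicity, the investigator's judgment of the patient's best interest, "The patient is beginning another treatment" and "Refusal of the patient to continue treatment or follow-up". The reason for withdrawal before progression must go on the case report form. An exit visit is required, and tumor response is among its procedures.

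**Assessments.** Section 5.3 opens its schedule with "The following tests and observations will be performed during the treatment phase of" the study and lists disease assessment at least every 9 weeks. Sections 3.3 and 6.2.2 leave imaging after the first response scan to the treating physician.

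**Follow-up.** Section 4.3 follows all enrolled patients for 30 days after the week 9 visit. Section 5.4 says "We will only follow patients who have experienced grade 3 or 4 adverse event or serious adverse event" related to the study medication, over the same 30 days; other patients are followed by institutional guidelines. Appendix 2, on symptomatic deterioration, says "Every effort should be made to document the objective progression even after discontinuation of treatment". Under Reporting of results it adds "All patients included in the study must be assessed for response to treatment, even if there are major protocol treatment deviations".

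**PFS.** The synopsis and sections 6.2.6 and 8.3 define the event as first recorded progression or death. Then: "If a patient does not progress or die while being followed via tumor assessment, progression-free survival will be censored" at the last disease assessment. Section 8.3 plans Kaplan-Meier medians by BRCA1 cohort. No sensitivity analysis is given, and neither new therapy nor symptomatic deterioration is addressed.

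**The concern.** Kaplan-Meier estimation assumes that a censored patient has the same outlook as those still at risk. Several of the withdrawal reasons in section 4.3 need not satisfy that. A patient taken off in her own interest, or moved to another therapy without a scan showing progression, is often close to progression or death. If she leaves and no later date is collected, a failure becomes a censored time.

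The censoring sentence adds a second difficulty. It can be read as counting a death only during tumor-assessment follow-up, although the event definition just before it counts death without that condition.

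PFS is the only secondary endpoint in section 3.1, and it is read by BRCA1 cohort. If such exits are more frequent in one cohort, the two medians are distorted by different amounts, and the difference could be mistaken for a BRCA1 effect.

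**Working it through.** **No plan figure to reproduce.** The documents give no PFS sample size, event count, power or withdrawal rate.

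**Inputs.** Median PFS 2.5 months (the literature figure in the synopsis and section 1.2), or 2.5 × 52/12 = 10.8 weeks. Scan interval 9 weeks (section 5.3), or 9 × 12/52 = 2.077 months. *Assumed:* exponential PFS, and a share f = 10, 20 or 30% of failures that end in exit without documented progression.

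**Share at risk of this.** The probability of failing before week 9 is q = 1 − 2^(−2.077/2.5) = 0.438. Such a patient, if she exits without an assessment, has only the baseline scan and is censored at time 0. The section 4.3 follow-up ends at 9 + 30/7 = 13.3 weeks (3.07 months). By then 1 − 2^(−3.07/2.5) = 57% would have failed, leaving about 43% with later events.

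**Censoring at the exit date.** The event hazard falls to (1 − f) times its true value, so the median is 2.5/(1 − f):
- 2.5/0.9 = 2.78
- 2.5/0.8 = 3.13
- 2.5/0.7 = 3.57

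**Censoring at the last scan.** Events keep their exact times; undocumented failures go back to the previous 9-weekly scan. Survival at week 9 is S9 = 0.562/(1 − 0.438f). At s months beyond week 9 it is S9 × [1 − (1 − f)(1 − 2^(−s/2.5))/(1 − 0.438f)]. Setting this to 0.5:

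| f | S9 | s (months) | median = 2.077 + s |
|---|---|---|---|
| 10% | 0.588 | 0.62 | 2.70 |
| 20% | 0.616 | 0.87 | 2.95 |
| 30% | 0.647 | 1.20 | 3.27 |

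**Exit visit records half of these failures as events.** Replace f by f/2 = 5, 10, 15%. Last-scan rule: 2.60, 2.70, 2.82. Exit-date rule: 2.5/0.95 = 2.63, 2.5/0.90 = 2.78, 2.5/0.85 = 2.94.

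**Progression seen only at 9-weekly scans (limiting case).** Survival at week 9 is S9, and at week 18 it is S9²:

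| f | week 9 | week 18 |
|---|---|---|
| 0 | 0.56 | 0.32 |
| 10% | 0.59 | 0.35 |
| 20% | 0.62 | 0.38 |
| 30% | 0.65 | 0.42 |

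The curve first drops below 0.5 at week 18 in every row, so the median does not move.

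**Other reasons for leaving (simulation, 400,000 patients, same exponential model).** Withdrawal unrelated to prognosis, censored at withdrawal: about 2.5 months. If 10, 20 or 30% of patients withdraw for toxicity, all from the half with longer PFS: 2.40, 2.30, 2.22 months, a downward bias.

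**Between cohorts.** With identical true PFS, and f = 10% in one cohort and 30% in the other, the false gap is 3.27 − 2.70 = 0.57 months (last scan) to 3.57 − 2.78 = 0.79 months (exit date). For scale, with 15 and 35 patients, identical PFS and no censoring, the simulated 95% range for the difference in medians is about −2.0 to +2.5 months.

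**The case against.** The case on the other side is substantial. A reader might infer several things that the documents do not support.

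- *That stopping the drug is defined as leaving the study.* It is not. Section 4.3 ties exit to progression or withdrawal and says patients may be withdrawn for the listed reasons. Section 3.3 ends treatment for intolerable toxicity without calling that exit.
- *That nothing is collected afterwards.* Section 4.3 follows everyone for 30 days after week 9, and Appendix 2 asks for progression to be documented after discontinuation.
- *That the exit visit can only move the censoring date.* It includes tumor response, so it can record an event.
- *That a known death after exit is excluded by rule.* The event definition counts death without condition; exclusion is only one reading of the censoring sentence.
- *That median PFS is certain to be biased upward.* Direction depends on why patients leave, and size depends on f, which the documents do not give.

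The impact is also limited: PFS is descriptive, with no test or decision rule, and the illustrative gap lies well within sampling noise.

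All of this stands, and it narrows the point without removing it. Reasons to stop treatment are still listed as reasons to leave the study. The 30-day follow-up in section 4.3 conflicts with section 5.4 and is not described as efficacy follow-up. Appendix 2 has no matching procedure in the body. The exit visit does not state that imaging is required, and a deteriorating or refusing patient may not attend. Noise does not excuse a systematic error that a larger successor trial could inherit.

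**Conclusion.** The concern holds as a risk of informative censoring, not as a demonstrated bias. Under the plan as written, exits linked to deterioration or a change of therapy can be censored at the last assessment, and for those exits an upward shift in median PFS is likely. On a true median of 2.5 months with f = 10 to 30%, the illustrative range runs from no shift (scan-only detection), through about 0.1 to 0.4 months (exit visit records half), to about 0.2 to 1.1 months (none recorded). These figures rest on exponential PFS and an assumed f.

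The contradiction among sections 4.3, 5.4 and Appendix 2, and the ambiguity over death after exit, need no assumption. The response-rate rule is not affected by this route. This is a cheap improvement to a secondary endpoint.

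**What to change.** 1. Reconcile sections 4.3, 5.4 and Appendix 2 on who is followed after treatment stops, for what and for how long.
2. In section 4.3, separate stopping study drug from withdrawing consent to follow-up. This concerns data collection only and changes no rule on when treatment stops.
3. For all enrolled patients who have not withdrawn that consent, abstract from routine records the date of first progression, the start of and reason for any new anticancer therapy, and the date of death.
4. In the synopsis and sections 6.2.6 and 8.3, delete the clause in the censoring sentence that limits events to the period of tumor-assessment follow-up. State that a known progression or death after drug stop is an event.
5. Report censoring reasons by BRCA1 cohort, using the withdrawal reasons that section 4.3 already requires on the case report form.
6. Add two sensitivity analyses: one counting exit for symptomatic deterioration, or a switch made for it, as an event; one censoring at the start of new therapy.

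The cost is protocol wording, a few form fields and chart abstraction, with no extra patients or procedures. The downside is that some progression dates will come from irregular routine scans or from time on a new therapy; the second sensitivity analysis shows how much the latter matters.
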